#### Hypothesis Testing

The null and alternative hypotheses for testing superiority of the Test lens relative to the Control lens with respect to photopic resolution acuity with a glare source are as follows:

$$H_0: \mu_T - \mu_C \geq 0$$
$$H_A: \mu_T - \mu_C < 0$$

Where,  $\mu_T$  represents the mean photopic resolution acuity (logMAR) for the Test lens and  $\mu_C$  represents the mean photopic resolution acuity (logMAR) for the Control lens. Statistical superiority will be declared if the upper bound of the adjusted 2-sided 95% confidence interval of the mean difference (Test – Control) is less than 0. A model-based point estimate of mean difference being -0.05 logMAR or more ( $\leq -0.05$  logMAR) will be considered clinically meaningful.

# Clinical Study Protocol

## Johnson & Johnson Vision Care, Inc.

### 14.6. Secondary Analyses

Superiority testing with respect to the secondary endpoints in phase 2 will be assessed on the Intent-to-Treat (ITT) population.

#### Photopic Contrast Sensitivity with a Glare Source

For photopic and mesopic contrast sensitivity, first the logarithm of contrast sensitivity will be calculated as  $\log CS = \log_{10}(1/(contrast\ threshold/100))$ , and then the area under the log contrast sensitivity function (AULCSF) will be calculated using logCS and the log (base 10) of each spatial frequency based on the trapezoidal rule per eye per subject for the analysis purpose.

The AULCSF for photopic contrast sensitivity will be analyzed under bright light conditions with a broadband light source (glare) using a linear mixed model with a normal distribution. Lens type, dominant eye, and the interaction of lens type by dominant eye will be included in the model as fixed effects and age as a covariate. The covariance of residuals between eyes within the same subject (R-side) will be modeled using Unstructured (UN) covariance structure. If the model does not converge, then a compound Symmetry (CS) covariance structure will be considered. The Kenward and Roger method will be used for the denominator degrees of freedom.

#### Hypothesis Testing

The null and alternative hypotheses for testing superiority of the Test Lens compared to the Control lens with respect to AULCSF for photopic contrast sensitivity with a broadband light source are presented below:

$$H_0: \mu_T - \mu_C \leq 0$$
$$H_A: \mu_T - \mu_C > 0$$

Where,  $\mu_T$  represents the mean AULCSF for the Test lens and  $\mu_C$  represents the mean AULCSF for the Control lens. Statistical superiority will be declared if the lower bound of the 2-sided 95% confidence interval of the mean difference (Test – Control) is larger than 0. A model-based point estimate of the mean difference being 0.06 log or more ( $\geq 0.06$  log) will be considered clinically meaningful.

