**Clinical Study Protocol**  
**Johnson & Johnson Vision Care, Inc.**

and effect size (i.e., mean difference). Power was estimated using a paired sample *t*-test (exact method) with a 2-sided type I error rate of alpha = 0.05 for the primary endpoint and a Bonferroni adjusted 2-sided type I error rate (alpha = 0.025) for each secondary endpoint. The calculation was performed using the POWER procedure in SAS Version 9.4. *Table 9* below shows the estimated statistical power under different scenarios. Given time and resource constraints, sixty subjects have been considered as the optimal number which demonstrated an acceptable level of statistical power under most assessed scenarios. Therefore, the plan is to enroll approximately 66 eligible subjects with 60 subjects targeted to complete the study.

Table 9: Power Analysis for the Primary and Secondary Hypotheses (Superiority Testing)

Endpoints	Mean Difference (Test - Control)	Standard Deviation (Test)	Standard Deviation (Control)	Correlation	Completed Subjects	Power
Primary Endpoint: Photopic Resolution Acuity with a Glare Source (converted to logMAR)	-0.05	0.08	0.09	0.3	50	93.0%
					60	96.5%
					70	98.3%
				0.5	50	98.2%
					60	99.4%
					70	99.8%
		0.10	0.11	0.3	50	79.5%
					60	86.4%
					70	91.2%
				0.5	50	90.8%
					60	95.1%
					70	97.5%
Secondary Endpoint: AULCSF for Mesopic Contrast Sensitivity with a Glare Source	0.06	0.13	0.13	0.3	50	67.2%
					60	76.3%
					70	83.2%
				0.5	50	82.6%
					60	89.6%
					70	93.9%
		0.15	0.15	0.3	50	53.5%
					60	62.6%
					70	70.4%
				0.5	50	69.6%
					60	78.5%
					70	85.2%
Secondary Endpoint: AULCSF for Photopic Contrast Sensitivity	0.06	0.11	0.11	0.3	50	82.5%
					60	89.5%
					70	93.9%
				0.5	50	93.5%
					60	97.1%
					70	98.7%

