#### **14.4. Level of Statistical Significance**

All planned analysis for this study will be conducted with an overall type I error of 5% using a gatekeeping testing strategy and Bonferroni adjustment. The primary analysis will be conducted with a two-sided type I error rate of 0.05. Alpha will be shared between the two secondary endpoints using Bonferroni method; each secondary hypothesis will be tested at the two-sided type I error of 0.025 (0.05/2). The secondary hypotheses will be assessed only when the primary hypothesis is met.

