#### Mesopic Contrast Sensitivity with a Glare Source

The AULCSF for mesopic contrast sensitivity testing under dim light conditions with a broadband light source (glare) will be analyzed, tested, and interpreted in the same manner as the analysis of the AULCSF for photopic contrast sensitivity.

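### Section 14.6 declares both secondary endpoints superior on a 95% confidence interval, although the plan allots each a two-sided alpha of 0.025, so the Bonferroni split is not applied.

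*Combined protocol and SAP*

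**What the plan says.** Section 14.4 (Level of Statistical Significance) states that all planned analyses are "conducted with an overall type I error of 5% using a gatekeeping testing strategy and Bonferroni adjustment". On the primary: "The primary analysis will be conducted with a two-sided type I error rate of 0.05". On order: "The secondary hypotheses will be assessed only when the primary hypothesis is met". On the secondaries, after naming the Bonferroni method: "each secondary hypothesis will be tested at the two-sided type I error of 0.025 (0.05/2".

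Section 14.2 (Sample Size Justification) uses the same split for the power analysis: "a Bonferroni adjusted 2-sided type I error rate (alpha = 0.025) for each secondary endpoint".

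Section 14.6 (Secondary Analyses, Hypothesis Testing) then gives the rule for photopic AULCSF: "Statistical superiority will be declared if the lower bound of the 2-sided 95% confidence interval of the mean difference" (Test minus Control) is above zero. For mesopic AULCSF it adds no separate rule; that endpoint "will be analyzed, tested, and interpreted in the same manner as the analysis of the AULCSF for photopic contrast sensitivity".

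The primary rule in Section 14.5 uses an adjusted two-sided 95% interval, which agrees with its alpha of 0.05. Section 14.6 contains no adjusted interval and no 97.5% interval.

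**The concern.** A two-sided interval at level 1 − alpha corresponds to a test at two-sided alpha. An alpha of 0.025 calls for a 97.5% interval; a 95% interval tests at 0.05. Section 14.6 therefore gives each secondary endpoint twice the alpha that Section 14.4 allots, and no text says which section governs.

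The gate does not make up the difference. It protects the secondaries while the primary null is true. Once the primary is met, two hypotheses are tested in parallel, and the alpha split is what controls error across them.

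At stake is whether a contrast-sensitivity superiority claim is made when a result falls between the two thresholds. Left open, that choice could be settled after unmasking. Table 9 would also describe a different test from the one Section 14.6 sets out.

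**Working it through.** **Inputs.** From Section 14.2 and Table 9: paired t-test, 60 completers, difference 0.06 for each secondary; SD per lens 0.13 or 0.15 (mesopic) and 0.11 or 0.13 (photopic); correlation between eyes 0.3 or 0.5. From Section 14.4: two-sided alpha 0.025 per secondary. From Section 14.6: a 95% interval, so alpha 0.05. The documents give no correlation between the photopic and mesopic test statistics; 0, 0.5 and 0.8 are assumptions that show a range.

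**Step 1: reproduce Table 9.** SD_diff = √(s1² + s2² − 2·ρ·s1·s2); noncentrality = (difference / SD_diff)·√n; power from the noncentral t distribution with n − 1 df.

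Example, SD 0.13 and ρ = 0.5:
- SD_diff = √(0.0169 + 0.0169 − 0.0169) = 0.13
- noncentrality = (0.06 / 0.13)·√60 = 3.575
- critical t at 59 df is 2.300 for alpha 0.025: power 89.6%, as printed
- critical t at 59 df is 2.001 for alpha 0.05: power 94.0%

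All secondary scenarios at 60 completers:

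| SD per lens | ρ | Table 9 | Recomputed, alpha 0.025 | Recomputed, alpha 0.05 |
|---|---|---|---|---|
| 0.11 | 0.3 | 89.5% | 89.5% | 94.0% |
| 0.11 | 0.5 | 97.1% | 97.1% | 98.6% |
| 0.13 | 0.3 | 76.3% | 76.3% | 84.4% |
| 0.13 | 0.5 | 89.6% | 89.6% | 94.0% |
| 0.15 | 0.3 | 62.6% | 62.6% | 73.1% |
| 0.15 | 0.5 | 78.5% | 78.5% | 86.2% |

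The cells for 50 and 70 completers, and all the primary cells at alpha 0.05, also match to the printed decimal. So 0.025 is the alpha the secondaries were designed on, and the 95% interval departs from it.

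**Step 2: family error, both secondary nulls true and the gate passed.** Nominal alpha sums to 0.05 + 0.05 = 0.10 under Section 14.6 and 0.025 + 0.025 = 0.05 under Section 14.4. With independent statistics:
- two-sided, 95% intervals: 1 − 0.95² = 0.0975
- two-sided, 97.5% intervals: 1 − 0.975² = 0.0494
- false superiority of Test only, 95% intervals: 1 − 0.975² = 0.0494
- false superiority of Test only, 97.5% intervals: 1 − 0.9875² = 0.0248

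With correlated statistics, from the bivariate normal distribution:

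| Assumed correlation | Two-sided, 95% | Two-sided, 97.5% | Test only, 95% | Test only, 97.5% |
|---|---|---|---|---|
| 0 | 9.75% | 4.9% | 4.9% | 2.5% |
| 0.5 | 9.1% | 4.7% | 4.5% | 2.3% |
| 0.8 | 7.8% | 4.0% | 3.9% | 2.0% |

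**Step 3: where the two rules disagree.** The smallest estimate that clears the bound is t·SD_diff/√60. For SD 0.11 and ρ = 0.5, SD_diff = 0.11, so it is 2.001·0.11/√60 = 0.028 with a 95% interval and 2.300·0.11/√60 = 0.033 with 97.5%. For SD 0.15 and ρ = 0.3, SD_diff = 0.177, and the values are 0.046 and 0.053. An estimate between the two values in a scenario is superior under Section 14.6 only.

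**The case against.** The strongest objection is directional. The hypotheses in Section 14.6 are one-directional and superiority is declared only on the lower bound, so the two-sided family error counts findings against the Test lens that the rule never declares. Counting only false claims for Test, two 95% intervals give at most 0.025 + 0.025 = 5%, which is within the overall figure in Section 14.4. That arithmetic is right. But Section 14.4 states its alphas as two-sided. On that scale the primary carries 2.5% in the favourable direction and the two secondaries together at most 2 × 0.0125 = 2.5%; Section 14.6 gives them up to 5%. The conflict with the stated 0.025 per endpoint remains.

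Second, the plan contradicts itself, and it is not known which section would be executed. That is fair: the doubled error arises if Section 14.6 is followed as written. It is, however, the only place that says when secondary superiority is declared.

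Third, the practical reach is limited, and this stands. Sections 2.3 and 14.6 also compare the point estimate with 0.06. Under every Table 9 scenario at 60 completers, the smallest estimate that clears a 97.5% interval is 0.033 to 0.053, below that margin, so a result reaching 0.06 is superior under both rules. What changes is a statement of statistical superiority for a smaller effect, and Section 14.6 allows that statement without reference to the margin.

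Finally, a 95% rule would make secondary power higher than printed. The mismatch with Table 9 therefore shows inconsistency, not a shortage of subjects.

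**Conclusion.** The concern holds: the rule is wrong as written. Section 14.6 tests each secondary endpoint at twice the alpha that Sections 14.2 and 14.4 allot, and the cross-reference carries the error to the mesopic endpoint. If it is followed, family error across the two secondary claims is about double the planned level on either way of counting. Power at 60 completers would be 73.1% to 98.6%, not the 62.6% to 97.1% in Table 9.

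The error figures assume that both secondary nulls are true, that the primary gate has been passed, and that the correlation between the two test statistics lies within the range shown. The contradiction itself needs none of these assumptions. The primary analysis and the gate are not affected. Because the discrepancy can decide a superiority claim, it should be resolved before the data are unmasked.

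**What to change.** In the Section 14.6 decision rule for photopic AULCSF, replace the two-sided 95% confidence interval with a two-sided 97.5% confidence interval, described as Bonferroni-adjusted. State the same interval explicitly for mesopic AULCSF so that it does not depend on the cross-reference alone.

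The cost is one number in the text. The critical t at 59 df moves from 2.001 to 2.300, which is the hurdle the plan already states in Section 14.4. Section 14.4, Table 9 and the target of 60 completers need no change, because Table 9 was computed at 0.025.

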#### Mesopic Contrast Sensitivity with a Glare Source

The AULCSF for mesopic contrast sensitivity testing under dim light conditions with a broadband light source (glare) will be analyzed, tested, and interpreted in the same manner as the analysis of the AULCSF for photopic contrast sensitivity.

### 14.7. Other Exploratory Analysis

Other exploratory analysis may be conducted at the discretion of the study responsible clinician.

# **Clinical Study Protocol**

## **Johnson & Johnson Vision Care, Inc.**

### **14.8. Interim Analysis**

This is a two-phase study and approximately 24 subjects will be enrolled in phase 1 with a target of 20 to complete. An interim analysis will be performed after all subjects completed phase 1 on the primary endpoints (see Section 14.5 for the details of the planned interim analysis). Other endpoints in phase 1 may be descriptive summarized. The interim analysis on the primary endpoints in phase 1 will be used to verify the glare light source. If the glare light source is found effective (e.g., the reduction in the estimated mean of contrast sensitivity due to the glare source is about 0.1 log units), the study can move to Phase 2. If the glare source has no effect, or obliterates the target, then phase 2 will not begin and the study will be terminated.

### **14.9. Procedure for Handling Missing Data and Drop-Outs**

Missing or spurious values will not be imputed. The count of missing values will be included in the summary tables and listings.

### **14.10. Procedure for Reporting Deviations from Statistical Plan**

The analysis will be conducted according to that specified in above sections. There are no known reasons for which it is planned to deviate from these analysis methods. If for any reason a change is made, the change will be documented in the study report along with a justification for the change.

## **15. DATA HANDLING AND RECORD KEEPING/ARCHIVING**

### **15.1. Electronic Case Report Form/Data Collection**

The Vision Assessments (photopic and mesopic contrast sensitivity, photopic resolution acuity) will be collected using the Cambridge Research Systems Metropsis system. This data will be generated as PDF files. The data from the Metropsis and all other study data will be captured on electronic case report forms (eCRFs) using the Bioclinica EDC system. An authorized data originator will enter study data into the eCRFs using the EDC system. Data collected on equipment that is not captured in EDC will be formatted to the specification of the JJVC database manager and sent to JJVC for analysis.

The source data from the Metropsis will be transferred by the site staff to JJVC in regular intervals to be reviewed by JJVC. The data will be uploaded to a cloud-based system, such as MBox, by the site staff. The uploaded data will be remotely source verified by the monitors in accordance to the timelines in the Clinical Monitoring Plan. The Metropsis source data will be stored at the site in accordance with Section 19 of this protocol. The Metropsis source data stored at the site will be stored confidentially and will only be accessible by study site staff. The source data stored at the site may be stored on an external protected drive or a protected shared drive.

External data sources for this study include: Not Applicable

# **Clinical Study Protocol**

## **Johnson & Johnson Vision Care, Inc.**

The clinical data will be recorded on dedicated eCRFs specifically designed to match the study procedures for each visit. Only specifically delegated staff can enter data on a CRF. Once completed, the eCRFs will be reviewed for accuracy and completeness and signed by the Investigator. The sponsor or sponsor's representatives will be authorized to gain access to the subject recordation for the purposes of monitoring and auditing the study.

Edit checks, electronic queries, and audit trails are built into the system to ensure accurate and complete data collection. Data will be transmitted from the clinical site to a secure central database as forms are completed or updated, ensuring information accuracy, security, and confidentiality. After the final database lock, the Investigator will be provided with Individual Patient Profiles (IPP) including the full audit trail on electronic media in PDF format for all of the study data. The IPP must be retained in the study files as a certified copy of the source data for the study.

The content and structure of the eCRFs are compliant with ISO14155:2020.

### **15.2. Subject Record**

At a minimum, subject record should be available for the following:

- subject identification
- eligibility
- study identification
- study discussion
- provision of and date of informed consent
- visit dates
- results of safety and efficacy parameters as required by the protocol
- a record of all adverse events
- follow-up of adverse events
- medical history and concomitant medication
- test article receipt/dispensing/return records
- date of study completion
- reason for early discontinuation of test article or withdrawal from the study, if applicable

The subject record is the eCRF or an external record. The author of an entry in the subject record must be identifiable. The first point of entry is considered to be the source record.

Adverse event notes must be reviewed and initialed by the Investigator.

### **15.3. Trial Registration on ClinicalTrials.gov**

This study will be registered on ClinicalTrials.gov by the Sponsor.

# **Clinical Study Protocol**

## **Johnson & Johnson Vision Care, Inc.**

### **16. DATA MANAGEMENT**

#### **16.1. Access to Source Data/Document**

The Investigator/Institution will permit trial-related monitoring, audits, IEC/IRB review and regulatory inspection(s) by providing direct access to source data/documents. Should the clinical site be contacted for an audit by an IEC/IRB or regulatory authority, JJVC must be contacted and notified in writing within 24 hours.

#### **16.2. Confidentiality of Information**

Information concerning the investigational product and patent application processes, scientific data or other pertinent information is confidential and remains the property of JJVC. The Investigator may use this information for the purposes of the study only. It is understood by the Investigator that JJVC will use information developed in this clinical study in connection with the development of the investigational product and therefore may disclose it as required to other clinical investigators and to regulatory agencies. In order to allow the use of the information derived from this clinical study, the Investigator understands that he/she has an obligation to provide complete test results and all data developed during this study to the Sponsor.

#### **16.3. Data Quality Assurance**

Steps will be taken to ensure the accuracy and reliability of data, include the selection of qualified investigators and appropriate clinical sites and review of protocol procedures with the Principal Investigator. The Principal Investigator, in turn, must ensure that all Sub-Investigators and clinical site personnel are familiar with the protocol and all study-specific procedures and have appropriate knowledge of the study article.

Training on case report form completion will be provided to clinical site personnel before the start of the study. The Sponsor will review case report forms for accuracy and completeness remotely during the conduct of the study, during monitoring visits, and after transmission to data management. Any data discrepancies will be resolved with the Investigator or designee, as appropriate.

Quality Assurance representatives from JJVC may visit clinical sites to review data produced during the study and to access compliance with applicable regulations pertaining to the conduct of clinical trials. The clinical sites will provide direct access to study-related source data/documents and reports for the purpose of monitoring and auditing by JJVC and for inspection by local and regulatory authorities.

#### **16.4. Data Monitoring Committee (DMC)**

Not applicable

# **Clinical Study Protocol**

## **Johnson & Johnson Vision Care, Inc.**

### **17. CLINICAL MONITORING**

The study monitors will maintain close contact with the Principal Investigator and the Investigator's designated clinical site personnel. The monitor's responsibilities will include:

- Ensuring that the investigation is being conducted according to the protocol, any subsequent versions, and regulatory requirements are maintained.
- Ensuring the rights and wellbeing of subjects are protected.
- Ensuring adequate resources, including facilities, laboratories, equipment, and qualified clinical site personnel.
- Ensuring that protocol deviations are documented with corrective action plans, as applicable.
- Ensuring that the clinical site has sufficient test article and supplies.
- Clarifying questions regarding the study.
- Resolving study issues or problems that may arise.
- Reviewing of study records and source documentation verification in accordance with the monitoring plan.

### **18. ETHICAL AND REGULATORY ASPECTS**

#### **18.1. Study-Specific Design Considerations**

Potential subjects will be fully informed of the risks and requirements of the study and, during the study, subjects will be given any new information that may affect their decision to continue participation. Subjects will be told that their consent to participate in the study is voluntary and may be withdrawn at any time with no reason given and without penalty or loss of benefits to which they would otherwise be entitled. Subjects will only be enrolled if the subject is fully able to understand the risks, benefits, and potential adverse events of the study and provide their consent voluntarily.

#### **18.2. Investigator Responsibility**

The Principal Investigator is responsible for ensuring that the clinical study is performed in accordance with the signed agreement, the investigational plan, section 4 of the ICH E6(R2) guidelines on Good Clinical Practice (GCP), and applicable regulatory requirements. GCP is an international ethical and scientific quality standard for designing, conducting, recording, and reporting studies that involve the participation of human subjects. Compliance with this standard provides public assurance that the rights, safety, and well-being of study subjects are protected, consistent with the principles of the Declaration of Helsinki 64th WMA General Assembly 2013 and that the clinical study data are credible. The Investigator must maintain clinical study files in accordance with section 8 of the ICH E6(R2) guidelines on Good Clinical Practice (GCP), and applicable regulatory requirements.

